10.7. Appendix 7: ECG Findings of Potential Clinical Concern

ECG Findings That May Qualify as AEs

- Marked sinus bradycardia (rate <40 bpm) lasting minutes.
 - New PR interval prolongation >280 msec.
 - New prolongation of QTcF to >480 msec (absolute) or by \ge 60 msec from baseline.
 - New-onset atrial flutter or fibrillation, with controlled ventricular response rate: ie, rate <120 bpm.
 - New-onset type I second-degree (Wenckebach) AV block of >30 seconds' duration.
 - Frequent PVCs, triplets, or short intervals (<30 seconds) of consecutive ventricular complexes.

ECG Findings That May Qualify as SAEs

- QTcF prolongation >500 msec.
- New ST-T changes suggestive of myocardial ischemia.
- New-onset left bundle branch block (QRS >120 msec).
- New-onset right bundle branch block (QRS >120 msec).
- Symptomatic bradycardia.
- Asystole:
 - In awake, symptom-free participants in sinus rhythm, with documented periods of asystole ≥3.0 seconds or any escape rate <40 bpm, or with an escape rhythm that is below the AV node.
 - In awake, symptom-free participants with atrial fibrillation and bradycardia with 1 or more pauses of at least 5 seconds or longer.
 - Atrial flutter or fibrillation, with rapid ventricular response rate: rapid = rate >120 bpm.
- Sustained supraventricular tachycardia (rate >120 bpm) ("sustained" = short duration with relevant symptoms or lasting >1 minute).
- Ventricular rhythms >30 seconds' duration, including idioventricular rhythm (heart rate <40 bpm), accelerated idioventricular rhythm (HR >40 bpm to <100 bpm), and

monomorphic/polymorphic ventricular tachycardia (HR >100 bpm (such as torsades de pointes)).

- Type II second-degree (Mobitz II) AV block.
- Complete (third-degree) heart block.

ECG Findings That Qualify as SAEs

- Change in pattern suggestive of new myocardial infarction.
- Sustained ventricular tachyarrhythmias (>30 seconds' duration).
- Second- or third-degree AV block requiring pacemaker placement.
- Asystolic pauses requiring pacemaker placement.
- Atrial flutter or fibrillation with rapid ventricular response requiring cardioversion.
- Ventricular fibrillation/flutter.
- At the discretion of the investigator, any arrhythmia classified as an adverse experience.

The enumerated list of major events of potential clinical concern are recommended as "alerts" or notifications from the core ECG laboratory to the investigator and Pfizer study team, and not to be considered as all inclusive of what to be reported as AEs/SAEs.

PFIZER CONFIDENTIAL

Final Protocol Amendment 1, 09 Nove	mber 2020
CCI	

PF-07258669 Protocol C4541001

CCI						
l						
I						

CCI						
	Ľ.					_

PFIZER CONFIDENTIAL

Page 88

10.10. Appendix 10: Abbreviations

The following is a list of abbreviations that may be used in the protocol.

Abbreviation	Term
Abs	absolute
AE	adverse event
ALP	alkaline phosphatase
ALT	alanine aminotransferase
CCI	
AST	aspartate aminotransferase
AUC	area under the curve
AUC ₂₄	area under the curve from time=0 to time=24 hours post dose
AUC _{last}	area under the plasma concentration-time profile from time 0 to the
	time of the last quantifiable concentration
AUCinf	area under the plasma concentration-time profile from time 0
	extrapolated to infinite time
AV	atrioventricular
β-hCG	beta-human chorionic gonadotropin
BMI	body mass index
BP	blood pressure
bpm	beats per minute
BUN	blood urea nitrogen
Ceff	efficacious concentration
CFR	Code of Federal Regulations
CIOMS	Council for International Organizations of Medical Sciences
СК	creatine kinase
CKD-EPI	Chronic Kidney Disease Epidemiology Collaboration
Clast	last quantifiable concentration
C _{max}	maximum observed concentration
CO ₂	carbon dioxide (bicarbonate)
COVID-19	Coronavirus Disease 2019
CRF	case report form
CRO	contract research organization
CRU	clinical research unit

Abbreviation	Term
CSR	clinical study report
СТ	clinical trial
CTMS	clinical trial management system
CCI	
DC	discontinuation
CCI	
DILI	drug-induced liver injury
DMC	data monitoring committee
C	
CI	
EC	ethics committee
ECG	electrocardiogram
eCRF	electronic case report form
EDP	exposure during pregnancy
EDR	extemporaneous dispensing record
eGFR	estimated glomerular filtration rate
EMA	European Medicines Agency
ET	early termination
EU	European Union
EudraCT	European Clinical Trials Database
C	
FSH	follicle-stimulating hormone
GCP	Good Clinical Practice
GGT	gamma-glutamyl transferase
GLP	Good Laboratory Practice
GPCR	G-protein coupled receptor
HBcAb	hepatitis B core antibody
HBsAb	hepatitis B surface antibody
HBsAg	hepatitis B surface antigen
HCVAb	hepatitis C antibody
HDL	high-density lipoprotein
HIPAA	Health Insurance Portability and Accountability Act
HIV	human immunodeficiency virus
HR	heart rate
HRT	hormone replacement therapy
IB	investigator's brochure
ICD	informed consent document
ICH	International Council for Harmonisation
ID	identification

Abbreviation	Term
IND	investigational new drug
INR	international normalized ratio
IPAL	Investigational Product Accountability Log
IQMP	integrated quality management plan
IRB	institutional review board
IV	intravenous
C	
C	
k _{el}	elimination rate constant
LBBB	left bundle branch block
LFT	liver function test
LDL	low-density lipoprotein
CCI	
MC1R	melanocortin-1 receptor
MC2R	melanocortin-2 receptor
MC3R	melanocortin-3 receptor
MC4R	melanocortin-4 receptor
MC5R	melanocortin-5 receptor
MCH	mean corpuscular hemoglobin
MCHC	mean corpuscular hemoglobin concentration
MCV	mean corpuscular volume
msec	millisecond
N/A	not applicable
NOAEL	no-observed-adverse-effect level
NOEL	no-observed-effect-level
PCR	polymerase chain reaction
PCRU	Pfizer clinical research unit
PD	pharmacodynamic(s)
PI	principal investigator
PIMS	Phase 1 Management System
PK	pharmacokinetic(s)
PR	pulse rate
PI PVC	prothrombin time
PVC	premature ventricular contraction/complex
QIC	corrected QT
QTcF	corrected QT (Fridericia method)
RBC	red blood cell

Abbreviation	Term
CCI	
SAE	serious adverse event
SAP	statistical analysis plan
SCr	serum creatinine
SoA	schedule of activities
SOP	standard operating procedure
SPF	sun protection factor
SRSD	single reference safety document
SUSAR	suspected unexpected serious adverse reaction
t _{1/2}	terminal half-life
TBili	total bilirubin
THC	tetrahydrocannabinol
T _{max}	time for C _{max}
CCI	
ULN	upper limit of normal
US	United States
UV	ultraviolet
WBC	white blood cell
WOCBP	woman of childbearing potential

Page 94

## 1. VERSION HISTORY

**Table 1. Summary of Changes**

Version/ Date	Associated Protocol Amendment	Rationale	Specific Changes
1 01 Feb 2021	Amendment 1 09 Nov 2020	N/A	N/A

## 2. INTRODUCTION

This statistical analysis plan (SAP) provides the detailed methodology for summary and statistical analyses of the data collected in Study C4541001. This document may modify the plans outlined in the protocol; however, any major modifications of the primary endpoint definition or its analysis will also be reflected in a protocol amendment.

Text in italics is taken directly from the protocol.

### 2.1. Study Objectives, Endpoints, and Estimands

Objectives	Endpoints
Primary:	Primary:

 
To evaluate the safety and tolerability of single ascending doses of PF-07258669 administered orally to healthy adult participants. To evaluate the safety and tolerability of single ascending doses of PF-07258669 administered orally to healthy adult participants.
 
	
 
Assessment of adverse events, clinical safety laboratory tests, vital signs, continuous cardiac monitoring, 12-lead electrocardiograms, respiratory rate, oral body temperature, physical examinations, and neurological examinations.
 

Secondary:	Secondary:

 
To evaluate the pharmacokinetics of PF-07258669 following single doses of PF-07258669 administered orally to healthy adult participants.
 
	
 
Pharmacokinetic (PK) parameters derived from plasma PF-07258669 concentrations: Cmax, AUClast, AUCinf, Tmax, and t½, if data permit.
 

CCI	

There are no estimands in this study.

## 2.2. Study Design

*This study is a randomized, investigator- and participant-blind, sponsor-open, placebo-controlled, first-in-human, single ascending oral dose study of PF-07258669 administered to healthy adult participants. Up to approximately 24 healthy adult participants (up to 3 cohorts of approximately 8 participants each) will be enrolled in this study. Each participant is planned to undergo 4 treatment periods receiving 3 doses of PF-07258669 and 1 dose of placebo.*

*Precautionary sentinel dosing will be used in each period of each cohort. Two participants (1 receiving PF-07258669 and 1 receiving placebo) within a period will be dosed initially before the remaining participants of that period are dosed. Safety and tolerability data through at least 24 hours post-dose for the sentinel participants will be reviewed prior to dosing the remaining participants of that period.*

[figure not shown]
*Dose levels will be escalated to bracket the expected clinical dose range, but projected exposures will not exceed the pre-defined human exposure limits. The optional third cohort will only be used if the objectives of the study are not fulfilled in Cohort 1 and Cohort 2. The total duration of participation from the screening visit to the telephone follow-up contact will be approximately 14 weeks.*

A starting dose of 0.1 mg of PF-07258669 is planned.

*If a participant drops out before completing all study periods within a cohort, or withdraws for reasons unrelated to the safety of the study intervention, the participant may be replaced at the discretion of the investigator and sponsor. The replacement participant(s) may or may not be required to complete all periods of the cohort in which they are participating at the discretion of the investigator and sponsor.*

Figure 1 shows the study design.

**Figure 1: Study Schema**

### 3. ENDPOINTS AND BASELINE VARIABLES: DEFINITIONS AND CONVENTIONS

### 3.1. Primary Endpoint(s)

The primary endpoints are the following safety endpoints:

- Adverse events,
- clinical safety laboratory tests,
- vital signs,
- continuous cardiac monitoring,
- 12-lead electrocardiograms (ECG),
- respiratory rate,
- oral body temperature,
- physical examinations,
- neurological examinations.

### 3.1.1. Adverse Events

All adverse events that start, or worsen in severity, on or after the date and time of the first dose but before the follow-up contact (28-35 days after last dose) will be flagged as Treatment-Emergent Adverse Events (TEAEs).

TEAEs will be assigned to the dose taken in the period they start in. Events that occur during a non-treatment period (for example, washout or follow-up) will be counted as treatment emergent and attributed to the most recent dose taken prior to the event.

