1.2. Schema

- Screening to dosing on Day 1 in Period 1: Maximum of 28 days for each cohort.
- Inpatient stay in each period: Day -1 to minimum of Day 3 (ie, 48 hours post-dose).
- In each period, 6 participants will be randomized to receive PF-07258669, and 2 participants will receive matching-placebo.
- Precautionary sentinel dosing will be used in each period of each cohort. Two participants (1 receiving PF-07258669 and 1 receiving placebo) within a period will be dosed initially before the remaining participants of that period are dosed. Safety and tolerability data through at least 24 hours post-dose for the sentinel participants will be reviewed prior to dosing the remaining participants of that period.
- The starting dose level in Period 1 of Cohort 1 is 0.1 mg. All other planned dose levels in other periods and cohorts may be adjusted pending emerging safety, tolerability, and PK data from previous periods and cohorts.
- On-site follow-up visit to occur on Day 8 ±2 days in Period 4 only, with an additional follow-up contact occurring 28-35 days after administration of the final dose of study intervention.

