Visit Identifier ^a	Screening		Period 1 to Period 4 ^b Follow-Up ET								ET/DC									
	Day -28	Day						Day	1						D	ay	Day	Visit:	Contact:	
	to Day -2	-1						-								2	3	Day	28-35	
Hours After Dose			0 ^d	0.17	0.5	1	1.5	2	4	6	8	10	12	16	24	36	48	8±2°	Days ^c	
Serum FSH ^r	Х																			
HBcAb, HBsAg, HBsAb, HCVAb, HIV testing	Х																			
Pfizer Prep B2 banked sample ^s			Х																	
Pfizer Prep D1.5 banked sample ^s			Х																	
PF-07258669 plasma pharmacokinetics			Х	Х	Х	Х	Х	Х	Х	Х	Х		Х	Х	Х	Х	Х			Х
CCI																				
Urine Samples for:																				
Urine drug test	Х	Х																		
Clinical safety laboratory tests ^q	Х	Х													Х		Х	Х		Х
Abbreviations: \rightarrow = ongoing/continuous event; AE = adverse event; BP = blood pressure; CRU = clinical research unit; DC = discontinuation; ECG = electrocardiogram;																				
ET = early termination; FSH = follicle stimulating hormone; HBcAb = hepatitis B core antibody; HBsAb = hepatitis B antibody; HBsAg = hepatitis B surface antigen;																				
HCVAb = hepatitis C antibody: HIV = human immunodeficiency virus: PR = pulse rate.																				

a. Day relative to start of study treatment (Day 1).

b. There will be a washout interval of ≥ 7 days between doses within an individual participant.

- c. Onsite follow-up visit to occur on Day 8 ±2 days in Period 4 only. Follow-up contact may occur via telephone contact and must occur 28-35 days after administration of the final dose of study intervention.
- d. Day 1 activities at time=0 hours are prior to the dose, except for study treatment administration.
- e. Participants may be confined to the CRU after completion of Day 3 activities at the discretion of the investigator or if safety, tolerability, or PK data dictate the need to prolong confinement in the CRU.
- f. Period 1 only. Review any changes from Screening.
- g. Contraception only required for male study participants and is recommended for partners of male study participants who are WOCBP.
- h. COVID-19 questionnaire includes check for suspected contact, risk zone, and COVID-19 related symptoms.
- i. Testing for active COVID-19 infection via testing for SARS-CoV-2 viral dosing (using PCR). To meet PCRU practice, testing for active COVID-19 infection will be performed at screening, admission, and follow-up visit.

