4.2. Scientific Rationale for Study Design

The population planned for this study will be healthy males and females of nonchildbearing potential. Female participants will be confirmed not to be of childbearing potential because embryo-fetal developmental toxicity studies with PF-07258669 have not been conducted. In male participants, appropriate measures are expected to be followed to minimize potential transfer of PF-07258669 via semen to partners (see Appendix 4).

Because this is the first time PF-07258669 will be administered to humans, an escalating single oral dose design is planned with careful assessment and ongoing review of safety, tolerability, and PK data of PF-07258669. Sentinel dosing will also be utilized in each period to ensure that safety and tolerability data in a subset of 2 participants within each period supports testing additional participants.

At each dose level, 6 participants are planned to receive PF-07258669 and 2 participants are planned to receive placebo with all participants at the end of the study having received 1 dose of placebo and 3 doses of PF-07258669. In addition, the highest anticipated C_{max} and AUC_{24} PF-07258669 will not exceed the pre-identified human exposure stopping limits nor exceed the highest feasible total daily dose of 2000 mg.

The design permits both within- and between-participant assessments of safety, tolerability, and PK. Furthermore, to permit an unbiased assessment of safety, the administration of both PF-07258669 and placebo in each period will be double-blinded to both site staff (except those involved in preparation of doses) as well as the participants.

PK samples are planned to be collected over 48 hours post-dose. However, sampling times, duration of sampling, and/or the length of the washout period may be modified and/or extended if data generated in previous periods indicate that the half-life is longer than predicted.

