8.3.1. Time Period and Frequency for Collecting AE and SAE Information

The time period for actively eliciting and collecting AEs and SAEs ("active collection period") for each participant begins from the time the participant provides informed consent, which is obtained before the participant's participation in the study (ie, before undergoing any study-related procedure and/or receiving study intervention), through and including a minimum of 28 calendar days, except as indicated below, after the last administration of the study intervention.

Follow-up by the investigator continues throughout and after the active collection period and until the AE or SAE or its sequelae resolve or stabilize at a level acceptable to the investigator and Pfizer concurs with that assessment.

For participants who are screen failures, the active collection period ends when screen failure status is determined.

If the participant withdraws from the study and also withdraws consent for the collection of future information, the active collection period ends when consent is withdrawn.

If a participant definitively discontinues or temporarily discontinues study intervention because of an AE or SAE, the AE or SAE must be recorded on the CRF and the SAE reported using the CT SAE Report Form.

Investigators are not obligated to actively seek AE or SAE after the participant has concluded study participation. However, if the investigator learns of any SAE, including a death, at any time after a participant has completed the study, and he/she considers the event to be reasonably related to the study intervention, the investigator must promptly report the SAE to Pfizer using the CT SAE Report Form.

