The investigator will make an assessment of intensity for each AE and SAE reported during the study and assign it to 1 of the following categories:

- Mild: An event that is easily tolerated by the participant, causing minimal discomfort and not interfering with everyday activities.
- Moderate: An event that causes sufficient discomfort and interferes with normal everyday activities.
- Severe: An event that prevents normal everyday activities. An AE that is assessed as severe should not be confused with an SAE. Severe is a category utilized for rating the intensity of an event; and both AEs and SAEs can be assessed as severe.

An event is defined as "serious" when it meets at least 1 of the predefined outcomes as described in the definition of an SAE, NOT when it is rated as severe.

Assessment of Causality

- The investigator is obligated to assess the relationship between study intervention and each occurrence of each AE/SAE.
- A "reasonable possibility" of a relationship conveys that there are facts, evidence, and/or arguments to suggest a causal relationship, rather than a relationship cannot be ruled out.
- The investigator will use clinical judgment to determine the relationship.
- Alternative causes, such as underlying disease(s), concomitant therapy, and other risk factors, as well as the temporal relationship of the event to study intervention administration, will be considered and investigated.
- The investigator will also consult the IB and/or product information, for marketed products, in his/her assessment.
- For each AE/SAE, the investigator **must** document in the medical notes that he/she has reviewed the AE/SAE and has provided an assessment of causality.

- There may be situations in which an SAE has occurred and the investigator has minimal information to include in the initial report to the sponsor. However, it is very important that the investigator always make an assessment of causality for every event before the initial transmission of the SAE data to the sponsor.
- The investigator may change his/her opinion of causality in light of follow-up information and send an SAE follow-up report with the updated causality assessment.
- The causality assessment is one of the criteria used when determining regulatory reporting requirements.

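### SAP 3.1.1 counts a worsening as treatment-emergent but assigns the dose by onset alone, so, unless a worsening opens a new AE record, one that follows a later dose is tabulated under the earlier treatment

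*SAP*

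**What the plan says.** SAP 3.1.1 defines the treatment-emergent flag with two arms, onset and worsening: "All adverse events that start, or worsen in severity, on or after the date and time of the first dose", up to the follow-up contact. The next sentence sets the dose by onset: "TEAEs will be assigned to the dose taken in the period they start in". A further sentence sends events in a non-treatment period, with washout and follow-up as its examples, to the most recent dose before the event. Screening is not named, and no sentence uses the date of a worsening.

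The surrounding design is as follows.

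- Protocol 4.2 plans a crossover, with "all participants at the end of the study having received 1 dose of placebo and 3 doses of PF-07258669".
- Protocol 1.3, footnote b: "There will be a washout interval of ≥ 7 days between doses within an individual participant".
- Protocol 1.2: "Inpatient stay in each period: Day -1 to minimum of Day 3". A period therefore begins before its dose is given.
- Protocol 8.3.1: active AE collection "for each participant begins from the time the participant provides informed consent", so AEs that begin during screening are recorded.
- Protocol 10.3.3: "The investigator will make an assessment of intensity for each AE and SAE reported during the study", using one of three categories. The same section has updated information entered in the CRF already completed. Neither statement says whether a worsening becomes a new AE record.
- SAP 6.1.1 lists and summarizes AEs by treatment under sponsor reporting standards that are not reproduced.

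**The concern.** The flag and the assignment rule use different events. A worsening can make an AE treatment-emergent, yet it plays no part in choosing the treatment column. In a parallel-group study this would matter little. Here each participant passes through placebo and three active doses, so the rule decides where within a person a deterioration is shown.

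Adverse events are a primary endpoint, and they also carry other primary endpoints. Telemetry has no summaries of its own (SAP 6.1.4), and its events of concern are reported as AEs (SAP 3.1.4). Untoward physical and neurological findings are likewise captured as AEs if they meet the definition (SAP 3.1.8). The measured safety endpoints take a fresh baseline in each period (SAP 3.1.2, 3.1.3 and 3.1.5 to 3.1.7), so a deterioration after a later dose is credited to that dose. AE worsening is handled differently, and the SAP gives no reason.

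**Working it through.** The plan gives no figure to reproduce. The check applies the text of SAP 3.1.1 to possible AE histories, assuming that one AE stays one record.

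| Onset | Worsening | Dose under SAP 3.1.1 | Last dose before the worsening (or onset, if none) |
|---|---|---|---|
| After Period 1 dose | After Period 2 dose | Period 1 only | Period 2 |
| Washout after Period 1 | After Period 2 dose | Period 1 only | Period 2 |
| Day -1 or pre-dose Day 1, Period 1 | After Period 1 dose | Period 1 | Period 1 |
| Day -1 or pre-dose Day 1, Period 1 | Only after Period 2 dose | Period 1 only | Period 2 |
| Screening | After Period 1 dose | None | Period 1 |
| Day -1 or pre-dose Day 1, Period 2 | None | Period 2 by the first assignment sentence, Period 1 by the second | Period 1 |

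The second row reads the event in the non-treatment sentence as its onset. Reading it as the worsening would cover only worsenings that fall in washout or follow-up, not those in a dosing period. In the last row both sentences can be claimed: the day lies inside Period 2 by the inpatient stay, and between doses by the washout footnote.

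**Opportunities by design.** Each period has 6 participants on active drug and 2 on placebo, and each participant receives placebo once. In a complete cohort of 8, 2 participants therefore have placebo in each of Periods 1, 2, 3 and 4.

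- Between-period transitions: 8 × 3 = 24.
- Placebo to active (placebo in Period 1, 2 or 3): 3 × 2 = 6.
- Active to placebo (placebo in Period 2, 3 or 4): 3 × 2 = 6.
- Active to active: 24 − 6 − 6 = 12.
- Total: 2 × 24 = 48 for two cohorts, 3 × 24 = 72 for three.

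These are opportunities, not expected events.

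**Weight of one participant.** At a dose level with 6 on active drug, 1/6 = 16.7 percentage points. If AE tables pool placebo (an assumption; the SAP states pooling only for plots), the placebo group is 2 × 8 = 16 or 3 × 8 = 24, and one participant is 1/16 = 6.3 or 1/24 = 4.2 points.

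**Illustration with one assumed AE, mild after placebo and severe after an active dose.**

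- Any severity: as written, active is 0/6. With the worsening counted under the active dose it is 1/6, and placebo is unchanged. The difference shifts by 16.7 points.
- Severe, if tables use severity at onset: 0 in both columns as written, and 1/6 active after the change. The shift is again 16.7 points.
- Severe, if tables use maximum severity and placebo is pooled (both assumptions): active minus placebo is −6.3 (n = 16) or −4.2 (n = 24) as written, and +16.7 after the change. The shift is 22.9 or 20.8 points.

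**The case against.** The strongest reply is that the outcome depends on standards the reader cannot see. If the sponsor standards or the CRF open a new record at worsening, that record has its own start and takes the right dose, and both worsening problems disappear. One intensity category per AE is compatible with this, and it is a natural way to program the worsening arm of the flag. This stands as a condition on the point. It is not an answer, because the instruction to enter updates in the completed CRF can be read the other way and neither passage settles it.

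Second, Protocol 10.3.1 makes an exacerbation of a chronic or intermittent pre-existing condition an AE in its own right, so that group is assigned correctly. For a screening-onset AE that worsens in Period 1, the only dose that precedes the worsening is the Period 1 dose. That gap is therefore mostly missing detail.

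Third, attribution by onset is a legitimate, prespecified convention, and an AE that began on placebo does belong to placebo. The 16.7-point shift in any-severity incidence arises because the alternative counts the AE a second time. That is fair. The weakness is that the convention hides the worsening which the SAP's own definition treats as treatment-emergent.

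A reader might go further and infer that drug effects will be systematically shifted onto placebo, or that dose escalation could rest on misplaced events. The documents do not support either inference. By design, placebo-to-active and active-to-placebo transitions are equal in number. The dose-escalation rules in Protocol 6.6.1 do not refer to the SAP attribution, and SAP 5 places the analyses after database lock.

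**Conclusion.** The point holds as a minor one, on the condition that neither the sponsor standards nor the CRF opens a new record at worsening. As written, an AE that worsens after a later dose appears only under the earlier treatment. The missing dose for screening-onset AEs and the overlapping sentences for pre-dose onset in Periods 2-4 are lesser gaps in the same paragraph.

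The effect is limited to the by-treatment AE tables. These are descriptive, no hypothesis is tested (SAP 5.1), and individual AEs are also listed. It is probably rare, because the AE must still be open at the next dose, at least 7 days after the previous one, and then worsen. The documents give no event rates, so 16.7 points is the weight of one participant among 6 and not an expected bias. The larger shifts for severe AEs rest on the further assumptions stated with them.

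**What to change.** Replace the assignment sentences in SAP 3.1.1 with one rule:

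> Each TEAE onset, and each increase in severity after a later dose, is assigned to the last dose given before that onset or increase. An increase in severity after a later dose is counted as a separate event under that dose, at the worsened severity; the original event stays under its own dose at the maximum severity reached before the later dose. If onset precedes the first dose, only the post-dose increases are counted.

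This also settles pre-dose onset in Periods 2-4, which takes the previous dose, and AEs with onset before the first dose that worsen more than once. If the sponsor standards already open a new record at worsening, a sentence saying so should be used in place of the separate-event wording.

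The cost is a short SAP edit and one programming rule. The date and time of a severity increase must be available, which the existing flag already requires. The drawback is that one AE can count under more than one treatment, so the AE tables need a footnote.
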